6.5.2. Disallowed Therapy

The following concomitant medications are not permitted during the study:

- Blood products such as RBCs, platelets, and fresh frozen plasma, except as required during a surgery or as clinically indicated in the setting of an emergency.
- Medications that may increase the risk of bleeding such as anti-platelet agents (eg, aspirin, clopidogrel); NSAIDs (eg, ibuprofen, naproxen); anticoagulants (eg, warfarin, apixaban), except for the management of FVIII activity increases >ULN (please also refer to [Section 6.5.1](#) and the “Management Guide for Elevated Factor VIII Activity Levels”). Low dose aspirin (<100 mg/day) and PRN use of NSAIDs are allowed where medically necessary. Please contact the sponsor’s medical monitor if there are any questions regarding the use of medications that may prolong bleeding.
- Where possible, medications with known hepatotoxicity should be avoided. The investigator should inform the sponsor’s medical monitor of any plan to administer a medication with known hepatotoxicity.
- Concomitant use of another investigational therapy (for guidance about COVID-19 vaccination, refer to [Appendix 9 \[Section 10.9.6\]](#)); concurrent participation in another interventional clinical study is not allowed.
- Bypassing agents (eg, factor VIIa, activated prothrombin complex concentrate) and nonfactor treatment (eg, emicizumab), except in situations where it is medically necessitated. Antifibrinolytics (aminocaproic acid or tranexamic acid) are also disallowed.

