8.1. Efficacy Assessments

8.1.1. Hemophilic Bleeding Episodes and Treatment

An eDiary, a handheld device, will be provided to all participants on Visit 1. The participants are required to enter any occurrence of hemophilic bleeding episodes (including date, time, location and etiology) and any exogenous FVIII replacement (including date, time, reason, and dose) required to treat the bleeds in the eDiary.

If bleeding episodes or treatments are not entered during the appropriate time window in the eDiary, participants should communicate all bleeds and all relevant infusion data not entered into the eDiary to the investigator (or appropriate site staff member), and data should be entered by the investigator (or appropriate site staff member) according to the process in place with appropriate source documentation in the participant's medical record. Non-FVIII treatments or procedures to treat bleeds, will be entered by the investigator (or appropriate site staff member) according to the process in place.

The site staff should counsel participants regarding late eDiary entries and emphasize the importance of being compliant with expected eDiary entries (eg, it helps monitor the participant's condition throughout the study) and of reporting all bleeds and all relevant infusion data to the site staff on a contemporaneous basis.

During the site visits, the investigator (or qualified designee) will review the eDiary with participants. Bleeding episodes and any related treatments will be reviewed to ensure consistency between the medical record and/or eDiary (and/or CRF).

In the event that a participant may have to resume FVIII prophylaxis treatment, prophylaxis FVIII infusion data will not have to be reported on the eDiary (or conveyed to the study site staff on a contemporaneous basis) after Week 78 (Visit 14). Bleeds and non-prophylactic infusions (eg, on-demand and preventative) should continue to be reported throughout the course of the study. Prescribed FVIII product information will continue to be captured (eg, change in regimen), by the site staff, according to the process in place.

Bleeding episodes requiring treatment with FVIII product (as recommended in the World Federation of Hemophilia guidelines)³⁹ will count toward the determination of bleeding episode frequency and the eDiary and/or medical record will serve as the source document for bleeding episodes. Definitions of bleeds are in [Appendix 7](#).

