8.2.7.2. Analysis of FVIII Inhibitor

During all study periods, blood samples will be collected for measurement of inhibitory antibodies against FVIII (inhibitors) as specified in the SoA section of the protocol.

The Bethesda-Nijmegen assay will be used. One BU is defined as the amount of inhibitor that results in 50% residual FVIII:C activity.

Both de novo inhibitors and clinically significant de novo inhibitors will be assessed and are defined based on the following criteria.

- A de novo FVIII inhibitor is defined as a positive central laboratory inhibitor result (inhibitor assay result > 0.6 BU) by the Nijmegen method of the Bethesda assay, in an individual with no prior history of FVIII inhibitors, that is confirmed in a second separately drawn specimen, at least 6 weeks later, that is also assayed at the central laboratory. A local laboratory result indicating possible presence of an inhibitor will prompt an unplanned inhibitor assessment at the central laboratory.
- A de novo inhibitor will be deemed clinically relevant if the occurrence is associated with either complete loss of previously attained FVIII transgene expression (return to baseline FVIII activity level) or the need for the participant to administer non-FVIII coagulation factor products (by-pass agents) in order to achieve efficacy when treating breakthrough bleeding episodes.

In the event of a confirmed inhibitor level for a participant, the study will be paused (no additional participant will be treated) until the circumstances for occurrence of the event are assessed and until notification of regulatory agencies if required. The trial re-start will only be possible after Regulatory Authority approval via substantial amendment, where applicable based on local/regional regulatory requirements.

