3.1.1. Total Annualized Bleeding Rate (Total ABR)

An eDiary, a handheld device, will be provided to all participants on Visit 1. Participants are required to enter any occurrence of hemophilic bleeding episodes (including date, time,

location, and etiology) and any exogenous FVIII replacement (including date, time, reason, and dose) required to treat the bleeds in the eDiary.

Definitions of bleeds are provided below.

Treated Bleed: An event necessitating administration of coagulation factor within 72 hours of signs or symptoms of bleeding (protocol definition, unless specifically referring to untreated bleed).

Untreated Bleed: A bleeding event not necessitating administration of coagulation factor within 72 hours of signs and symptoms of bleeding.

New Bleed:

- A ‘new treated bleed’ is a bleed necessitating treatment (as described above) occurring >72 hours after stopping treatment from the original bleed for which treatment was initiated or a bleed necessitating treatment (as described above) occurring at a different site from the original bleed regardless of the time from last injection.
- A bleed is considered a ‘new untreated bleed’ if it does not necessitate treatment and occurring >72 hours after the previous untreated bleed at the same site or occurring >72 hours after stopping treatment from the original bleed for which treatment was initiated, or an untreated bleed occurring at a different site from the original bleed regardless of the time from last bleed or last injection.

If a bleed is treated with FVIII infusion (as indicated in the bleeding log of the eDiary) within 72 hours (by comparing date/time of bleeding to date/time of infusion in the eDiary), regardless of the type of treatment (preventive, prophylaxis or on demand), it will be considered as a treated bleed. If a bleed is not treated with FVIII infusion, as indicated in the eDiary bleeding log, the bleed will be considered as an untreated bleed. Table 6 provides a summary of bleeds that are considered treated/untreated bleeding events based on the data captured within the eDiary.

Table 6. Treated Bleeds / Untreated Bleeds Based on eDiary Data

Factor infusion was used to treat the bleed? (reported in eDiary bleeding log)	Any FVIII infusion within (\leq) 72 hours post bleeding?	Treated/Untreated bleed
Yes	Yes (regardless of reason)	Treated bleed
Yes	No	Untreated bleed
No	Yes (regardless of reason)	Untreated bleed
No	No	Untreated bleed

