4	Superiority in AIR from Week 12 [Day 78] through at least 15 months (up to data cutoff) postinfusion compared to prior prophylaxis treatment
5	Superiority in Annualized FVIII consumption (IU/kg) from Week 12 [Day 78] through at least 15 months (up to data cutoff) postinfusion compared to prior prophylaxis treatment
6	Superiority in Treated ABR from Week 12 [Day 78] through at least 15 months (up to data cutoff) postinfusion compared to prior prophylaxis treatment
7	Superiority in Total ABR from Week 12 [Day 78] through at least 15 months (up to data cutoff) postinfusion compared to prior prophylaxis treatment

8	Haem-A-QoL Physical Health domain score significantly improved from baseline at 12 months postinfusion
9	HAL Complex Lower Extremity Activities domain score significantly improved from baseline at 12 months postinfusion

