6.6.4. Immunogenicity

Percentage of participants with positive/negative interferon gamma (IFN γ) to each AAV or FVIII pool, FVIII overall and capsid overall, compare to baseline, will be summarized by the specified sampling timepoint for participants in whom the corticosteroid treatment is initiated.

Descriptive summaries will be provided for nAb to AAV titer by study visit. Number and percentage of participants with positive nAb to AAV will be summarized by study visit. Unscheduled assessments will also be presented. Data will also be presented in a listing.

Descriptive summaries will be provided for ADA by study visit. Number and percentage of participants with positive ADA will also be summarized by study week. Unscheduled assessments will also be presented. Data will also be presented in a listing.

One line plot will be generated, plotting FVIII activity level at Week 52 based on central chromogenic assay against ADA titer at Screening visit and ADA titer at Week 52, respectively.

Number and percentage of participants with FVIII inhibitor by the Bethesda Assay will be summarized by study visit.

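### SAP 3.1.1 defines a treated bleed by any coagulation factor but scores it by FVIII infusion alone, so bleeds treated only with a by-pass agent leave Treated ABR

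*SAP*

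**What the plan says.** **Definition.** SAP 3.1.1, like protocol Appendix 7, describes a treated bleed as "An event necessitating administration of coagulation factor within 72 hours of signs or symptoms of bleeding".

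**Algorithm.** The same SAP section then classifies bleeds by FVIII alone: "If a bleed is not treated with FVIII infusion, as indicated in the eDiary bleeding log, the bleed will be considered as an untreated bleed". In Table 6, a bleed with factor use logged but no FVIII infusion within 72 hours is untreated. With factor use logged and any FVIII within 72 hours, for whatever reason, it is treated.

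**By-pass agents.** Protocol 6.5.2 lists as not permitted "Bypassing agents (eg, factor VIIa, activated prothrombin complex concentrate) and nonfactor treatment (eg, emicizumab), except in situations where it is medically necessitated". Protocol 8.2.7.2 treats them as coagulation factor products. One of its two alternative criteria for a clinically relevant inhibitor is "the need for the participant to administer non-FVIII coagulation factor products (by-pass agents) in order to achieve efficacy when treating breakthrough bleeding episodes"; the other is complete loss of transgene expression. Protocol 8.1.1 provides for recording: "Non-FVIII treatments or procedures to treat bleeds, will be entered by the investigator" or other site staff. The same section also says that bleeds needing FVIII product count toward bleeding frequency.

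**Where the label matters.** Treated ABR is tested for noninferiority at step 3 of SAP Table 8 and again at step 6: "Superiority in Treated ABR from Week 12 [Day 78] through at least 15 months". SAP 3.2.9 reports the percentage of participants without treated bleeds.

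**Inhibitor reporting.** Protocol 8.2.7.2 states: "Both de novo inhibitors and clinically significant de novo inhibitors will be assessed and are defined based on the following criteria". SAP 6.6.4 plans: "Number and percentage of participants with FVIII inhibitor by the Bethesda Assay will be summarized by study visit".

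**The concern.** The two halves of SAP 3.1.1 disagree about one kind of bleed. A programmer following Table 6 scores a by-pass-only bleed as untreated, although the definition a few lines above makes it a treated bleed.

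The error runs in one direction. Inhibitor history is an exclusion criterion (protocol 5.2), so by-pass-only bleeds are expected almost entirely after infusion. Dropping them lowers the postinfusion Treated ABR and leaves the prophylaxis comparator untouched. A participant whose bleeds no longer respond to FVIII could then contribute nothing to Treated ABR and appear among those without treated bleeds.

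At stake are the Treated ABR estimate and the step 6 superiority test, which also opens steps 7 to 9.

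**Working it through.** The plan gives no figure on this point, so there is none to reproduce. The check is a comparison of rules, followed by illustrative arithmetic.

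**1. Definition against algorithm**

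| Treatment of the bleed within 72 hours | Definition | Table 6 |
|---|---|---|
| FVIII, factor use logged | Treated | Treated |
| FVIII and by-pass agent, factor use logged | Treated | Treated |
| By-pass agent only | Treated | Untreated |
| No factor of any kind | Untreated | Untreated |

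Only the third row conflicts. Total ABR counts treated and untreated bleeds alike, so the label does not matter there.

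**2. Effect per bleed**

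Inputs: at least 50 dosed participants (protocol 9.2); minimum postinfusion window Day 78 to Day 455 (SAP 3.1.1), which is 455 − 77 = 378 days, or 378/365.25 = 1.035 years.

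Shift in mean Treated ABR = k / (n × years), where k is the number of by-pass-only bleeds (assumed).

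- k = 1: 1 / (50 × 1.035) = 0.019 bleeds/year (0.014 at n = 70)
- k = 5: 0.097
- k = 20: 0.387
- Bleeds needed to shift the mean by the 3.0 margin: 3.0 × 50 × 1.035 ≈ 155

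**3. Effect on the percent reduction**

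Inputs: treated ABR of 4 before and 1 after infusion (protocol 9.2). Assume one participant in 50 has r by-pass-only bleeds/year and no other treated bleeds. The value 23.3 is the on-demand treated rate in the inhibitor study in protocol Table 3; 3 and 5 are assumptions.

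Mean by definition = (49 × 1 + r)/50. Mean under Table 6 = 49/50 = 0.98. Reduction = 1 − mean/4.

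| r per year | Mean by definition | Reduction by definition | Reduction under Table 6 |
|---|---|---|---|
| 3 | 1.04 | 74.0% | 75.5% |
| 5 | 1.08 | 73.0% | 75.5% |
| 23.3 | 1.446 | 63.9% | 75.5% |

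**4. Effect on the tests**

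Simulation of 20,000 trials: n = 50, one year per period, negative binomial counts with means 4 and 1, independent periods, and a Wald 95% CI on paired differences. One participant has bleeds at rate r, counted in full or set to zero. Dispersion is assumed.

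Noninferiority held in every simulated trial under both rules. Superiority pass rates, by definition / under Table 6:

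| r per year | Dispersion 0.5 | Dispersion 1 | Dispersion 2 |
|---|---|---|---|
| 5 | 100% / 100% | 99.9% / 100% | 97.6% / 98.6% |
| 10 | 100% / 100% | 99.8% / 100% | 95.4% / 98.5% |
| 23.3 | 99.1% / 100% | 95.5% / 100% | 82.0% / 98.8% |

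A separate run at 3 bleeds/year and dispersion 2 gave 97.9% / 98.4%. The Table 6 figures differ between rows only through simulation noise.

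**The case against.** **The FVIII-only rule has a basis in the protocol.** Protocol 8.1.1 ties bleed counting to treatment with FVIII product, so the SAP follows one of two protocol readings. This stands. The inconsistency lies in both documents, and correcting the SAP alone would leave it at odds with 8.1.1.

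**Most bleeds in such a participant may still count.** If FVIII is tried first and logged, the bleed stays treated even when a by-pass agent follows. This stands and limits the point to by-pass-only bleeds.

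**The large figure is an extreme case.** A rate of 23.3 comes from an arm without prophylaxis and would have to persist all year, with every bleed by-pass-only. Nonfactor treatment is allowed when medically necessary, which makes that unlikely. The simulation also uses a paired Wald interval with zero correlation, not the planned GEE negative binomial model or the planning correlation of 0.2. This stands: the pass rates are indicative only.

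**The timing data may be incomplete.** Protocol 8.1.1 asks for date and time for FVIII entries but states neither for non-FVIII treatments, and protocol 6.5 lists only dates for concomitant therapy. This stands, and the fix allows for it.

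**A reader might infer that the plan hides clinically relevant inhibitors altogether.** The documents do not support that. Confirmed inhibitors are medically important events reported as SAEs and events of special interest (protocol 10.3.2 and 8.3.8), and SAP 6.6.1 tabulates both. SAP 6.1.1.3 lists FVIII activity, bleeds and FVIII infusions for clinical review of treatment failure. SAP 6.6.2 plots each participant, and SAP 6.5.4 summarises concomitant medication other than FVIII. None of these carries a clinical-relevance flag, but the participants are visible. Nor do by-pass-treated bleeds by themselves define relevance, since loss of expression alone is enough.

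**Conclusion.** The contradiction within SAP 3.1.1 is real. Followed as written, Table 6 removes by-pass-only bleeds from Treated ABR and from the count of participants with treated bleeds, to the advantage of the gene therapy.

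The effect is conditional and probably small. No confirmed inhibitor arose among the 11 participants dosed in Phase 1/2 (protocol 2.3.1), and entry requires at least 150 exposure days. With one affected participant at 3 to 5 by-pass-only bleeds/year, the reduction is overstated by 1.5 to 2.5 percentage points and superiority barely changes. A material loss in the superiority pass rate appears only at the extreme rate, and most clearly with high dispersion. These sizes rest on the planning rates of 4 and 1, on n = 50, and on assumed bleed counts and dispersion.

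The documents do not support the stronger inference that the trial's main conclusions are at risk: the primary Total ABR and both noninferiority conclusions are unaffected. The lack of a relevance flag in SAP 6.6.4 is a reporting gap and would not by itself justify a change.

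**What to change.** 1. In the treated-bleed rule of SAP 3.1.1 and in Table 6, replace *FVIII infusion* with *coagulation factor infusion (FVIII or by-pass agent, from the eDiary or the site-entered record; use the date when the time is not recorded)*.
2. Align the protocol 8.1.1 sentence on bleeds treated with FVIII product with the Appendix 7 definition, so that both documents state one rule.
3. Optional, for reporting only: in SAP 6.6.4, add the number of participants with a confirmed de novo inhibitor and with a clinically relevant one, as protocol 8.2.7.2 defines them.

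The cost is one SAP wording change, one conforming protocol clarification and, if wanted, one table line. Non-FVIII bleed treatments are already entered by the sites; the only data limitation is that their times may not be recorded. The change should be made before database lock, so that no such bleed is classified after its effect is known.

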6.7. COVID-19 Related Data

In the event that any of the safety and/or efficacy related postinfusion procedures for ECG, liver ultrasound, HJHS, or PROs cannot be performed according to the timepoints specified in the study protocol, due to coronavirus disease 2019 (COVID-19) restrictions or otherwise, it is recommended that they be performed at the next subsequent on-site visit or unplanned visit. Even though the procedures may have been performed at a subsequent visit, any procedures not performed according to the timepoints specified in the study protocol are still considered protocol violations.

The impact of COVID-19 on C3731003 is expected to be minimal. The related data will be provided in the following data listings:

- Protocol deviations related to COVID-19.
- COVID-19 related adverse events will be listed with SOC and PT.
- Any study discontinuation due to COVID-19 related AEs, SAEs or death related to COVID-19.

7. INTERIM ANALYSES

7.1. Introduction

No formal interim analysis will be performed. This study will use an external Data Monitoring Committee (eDMC). The eDMC is independent of the study team and includes only external members. The eDMC will convene approximately every 6 months until study completion to monitor the safety and efficacy of the participants. Ad-hoc meetings will be organized as needed [eg, to assess events of special interest or after receipt of a Serious Unexpected Suspected Adverse Reaction (SUSAR)]. Specification details for the process and the outputs to be generated for eDMC review will be provided in the eDMC charter.

7.2. Interim Analyses and Summaries

Not applicable.

9. APPENDICES

Appendix 1. Statistical Methodology Details

Appendix 1.1. Specification for ABR Analysis Model and Parameters

The specific model parameters are:

- Response variable: observed number of bleeds, Y_i , where Y_i is assumed to follow negative binomial distribution
- Link function: Identity; $E[Y_i] = \mu_i = \eta_i$
- Linear predictor model: the mean number of bleeds is proportional to the observed duration, allowing for a different ABR per treatment;

$$\eta_i = \beta_1 \cdot t_i + \beta_2 \cdot I(\text{Treatment}) \cdot t_i; \quad t_i = \text{duration of observation in years}$$

- Assumed variance-covariance: The working correlation is assumed as *unstructured*, so that the variance of Y_i is given by:

$$V(Y_i) = \begin{bmatrix} \sigma_{11} & \sigma_{12} \\ \sigma_{12} & \sigma_{22} \end{bmatrix}.$$

Since there are only two data points per participant, many assumptions for the working correlation except for independence will result in the same estimate.

- The log link is commonly used in the generalized linear mixed model for the count data with a negative binomial distribution. However, identity link could also be applied to model count data, for Poisson distribution¹ and negative binomial distribution² when rate difference is of interest. The identity link was chosen to match the analysis goal, the testing of non-inferiority based on the difference in annualized bleeding rates (ABRs) between the two treatments for the participants that received different treatments before and after rather than the ratio of the two. In the above linear predictor model, β_2 represents the ABR difference.

Appendix 1.2. Example of SAS Code for Repeated Measure Additive Negative Binomial Regression Model

```
proc genmod data=main;
class trt subjid;
model bleeds = years years*trt/link=identity dist=negbin noint;
repeated subject=subjid;
estimate 'diff' years*trt 1 -1/alpha=0.05;
estimate 'Prophy' years 1 years*trt 0 1 / alpha=0.05;
estimate 'GTx' years 1 years*trt 1 0 / alpha=0.05;
Run;
```

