5.1. Hypotheses and Decision Rules

In this study, all hypothesis testing will be one-sided with Type I error of 0.025.

The primary objective is to evaluate the efficacy of a single infusion of PF-07055480 in participants ≥ 18 and < 65 years of age with moderately severe to severe hemophilia A (FVIII:C $\leq 1\%$).

For the primary efficacy analysis, the hypothesis testing written in statistical notation is:

H_0 : Total ABR_{PF-07055480} – Total ABR_{FVIII prophylaxis} ≥ 3.0 versus H_a : Total ABR_{PF-07055480} – Total ABR_{FVIII prophylaxis} < 3.0

where Total ABR_{PF-07055480} represents the mean Total ABR post PF-07055480 infusion, while Total ABR_{FVIII prophylaxis} represents the mean Total ABR on prior routine prophylaxis FVIII replacement. The proposed non-inferiority margin is 3.0 bleeds/year.

If the upper bound of the confidence interval of the difference (Total ABR_{PF-07055480} – Total ABR_{FVIII prophylaxis}) is less than 3.0, the noninferiority would be demonstrated.

For the key secondary endpoint (FVIII activity level $> 5\%$), the percentage of participants with FVIII activity level at 15 months post PF-07055480 infusion will be compared to the null hypothesis of percentage $\leq 68\%$ using an exact test for binomial proportion. The other key secondary endpoint (Treated ABR) will be tested for noninferiority using the same method and margin as described above for the Total ABR.

A gatekeeping process will be applied to control for multiple endpoint comparisons at the primary analysis. The subsequent hypothesis testing will only be performed after success on the previous hypothesis test. The testing ceases when a failure occurs. The sequence of gatekeeping process is displayed in Table 8 below. Note that only selected endpoints are included in the sequence.

Table 8. Gatekeeping Sequence

Order in the testing sequence	Statistical testing
1	Non-inferiority in Total ABR from Week 12 [Day 78] through at least 15 months (up to data cutoff) postinfusion compared to prior prophylaxis treatment with a NI margin of 3
2	Percentage of participants with FVIII activity $> 5\%$ at 15 months postinfusion compared to the null hypothesis of percentage $\leq 68\%$
3	NI in Treated ABR from Week 12 [Day 78] through at least 15 months (up to data cutoff) postinfusion compared to prior prophylaxis treatment with a NI margin of 3

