6.1. Primary Endpoint

6.1.1. Total Annualized Bleeding Rate

6.1.1.1. Main Analysis

Total ABR will be analyzed using a repeated measures generalized linear model with negative binomial distribution, identity link function and generalized estimating equation (GEE) model form to account for within-participant correlation. Number of bleeds within

the given follow-up period will be the dependent variable in the model. ‘Year’ and an interaction of year by treatment (treatment of prophylaxis or PF-07055480) will be included in the model. ‘Year’ is a numeric measure of time in the unit of year in the given follow-up period. ‘Treatment’ will be a class factor in the model, and ‘subject’ (i.e., participant) will be a random effect. No other covariates will be included in the model. Detailed specification for the model and parameters is provided in [Appendix 1.1](#).

- The ‘Efficacy’ population will be the main analysis population for the primary analysis.
- The Total ABR from Week 12 [Day 78] through at least 15 months (up to data cutoff) post PF-07055480 infusion will be compared to participants’ Total ABR on prior FVIII prophylaxis regimen before infusion. The estimation of difference and CI will be constructed. If the upper bound of the confidence interval of the difference of (Total ABR _{PF-07055480} – Total ABR _{FVIII prophylaxis}) is less than 3.0, then statistical significance of the noninferiority would be demonstrated. An example of SAS code of such analysis is included in [Appendix 1.2](#). If noninferiority is demonstrated, further testing for superiority would be conducted, using the same method, except the margin would be set to 0.

The summary table will include two columns, for FVIII prophylaxis (pre-PF-07055480) and PF-07055480 (post-PF-07055480), respectively. The descriptive statistics including n, mean, standard deviation, median, Q1, Q3, min, max of the observed Total ABR, estimated means with 95% CI of estimated means (model derived), estimated difference in mean Total ABRs (model derived), one-sided p-value, and the 95% CI of the difference in mean Total ABRs (model derived) will be presented in the summary table. In addition, percent reduction in mean Total ABR, one-sided p-value, and the corresponding 95% CI will be estimated from a separate analysis model with log link function. An example of SAS code for this analysis model is provided in [Appendix 1.3](#).

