Appendix 1.3. Example of SAS Code for Calculating Percent Reduction in Mean ABR

```
proc genmod data=main;
class trt subjid;
model bleeds = trt /offset=lyears dist=negbin link=log alpha=0.05;
** offset=log of years **;
repeated subject=subjid/ Type=UN;
estimate 'log diff' trt 1 -1 / exp;
ods output estimate=ci_ratio;
run;

data ci_reduction;
set ci_ratio;
where Label= "Exp(log diff)";
Percent_reduction = (1- LBetaEstimate)*100;
Lower_bound = (1- LBetaUpperCL)*100;
Upper_bound = (1- LBetaLowerCL)*100;
run;
```

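### Run as coded, the noninferiority interval for the ABR difference exceeds the stated one-sided 0.025 at the margin with about 50 participants if bleed counts are overdispersed

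*SAP*

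**What the plan says.** SAP 5.1 states: "In this study, all hypothesis testing will be one-sided with Type I error of 0.025". Noninferiority is declared when the upper confidence bound for the ABR difference (after minus before infusion) is below 3.0. Total ABR is step 1 of the testing sequence in SAP Table 8. Treated ABR, step 3, "will be tested for noninferiority using the same method and margin as described above for the Total ABR". After noninferiority on Total ABR, "further testing for superiority would be conducted, using the same method, except the margin would be set to 0" (SAP 6.1.1.1).

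SAP 6.1.1.1 describes an identity-link negative binomial GEE and refers to Appendix 1.2 for code. It also says that participant "will be a random effect. No other covariates will be included in the model". Appendix 1.1 says that the bleed count "is assumed to follow negative binomial distribution". It specifies an unstructured working correlation and adds that "many assumptions for the working correlation except for independence will result in the same estimate". The Appendix 1.2 code has "repeated subject=subjid" with no correlation option, whereas Appendix 1.3, for the percent-reduction model, has "repeated subject=subjid/ Type=UN".

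Protocol 9.2 reports power for at least 50 participants with an assumed correlation of 0.2. It gives no dispersion value and no type I error at the margin. Neither document names a small-sample correction or a t reference distribution.

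**The concern.** An uncorrected sandwich standard error with a normal quantile is a large-sample device. With about 50 participants and overdispersed counts, the estimated difference and its estimated standard error tend to be low together: a sample that happens to contain few heavy bleeders after infusion gives a favourable estimate and a short interval. That pushes error into the tail that decides noninferiority. Total ABR noninferiority is the first test, on which all later ones depend, so its stated error rate should be the one that the method delivers. The missing correlation option in the code for that same test raises the separate question of whether it matters numerically.

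**Working it through.** **Inputs.** Margin 3.0 and one-sided 0.025 (SAP 5.1). n = 50; correlation 0.2; Total ABR 5 before and 2 after; Treated ABR 4 and 1 (Protocol 9.2). Preinfusion follow-up 0.5 year, the minimum. Postinfusion Day 78 to Day 455 (SAP 3.1.1): 378/365.25 = 1.035 years. Assumed, because not in the documents: dispersion k, where Var(Y) = μ + kμ², and gamma frailty (the negative binomial case).

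**What the code computes.** With equal follow-up across participants, the model reduces to a paired comparison. Let d = Y_post/t_post − Y_pre/t_pre for each participant. The estimate is the mean of d, SE = √Σ(d − mean)²/n, and noninferiority is declared if mean + 1.96·SE < 3.

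**Scale at the margin (5 versus 8, k = 1).**
- Before: μ = 5 × 0.5 = 2.5; Var(Y) = 2.5 + 2.5² = 8.75; variance of the rate = 8.75/0.5² = 35.0.
- After: μ = 8 × 1.035 = 8.28; Var(Y) = 8.28 + 68.5 = 76.8; variance of the rate = 76.8/1.035² = 71.7.
- Covariance = 0.2 × √(35.0 × 71.7) = 10.0. Var(d) = 35.0 + 71.7 − 20.0 = 86.7. SE = √(86.7/50) = 1.32.

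The right-skewed postinfusion rate dominates the variance. At equal rates of 5 the postinfusion variance is about 29.8 against 35.0 before, so the two skews largely offset.

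**The plan's own figure.** Simulated noninferiority power with n = 50 is at least 99% at 5 versus 2 and at 4 versus 1, for every k tried from 0 to 5. This agrees with the stated figure of at least 95%.

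**Size at a true difference of exactly 3** (n = 50; 40,000 trials per cell; Monte Carlo SE about 0.1 point). The opposite tail is for fixed follow-up.

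| Scenario | k | Fixed follow-up | Varying follow-up | Opposite tail |
|---|---|---|---|---|
| Total, 5 to 8 | 0 | 2.8% | 2.8% | 3.0% |
| | 0.5 | 3.6% | 3.6% | 2.3% |
| | 1 | 3.9% | 4.3% | 2.0% |
| | 2 | 4.7% | 4.8% | 1.4% |
| Treated, 4 to 7 | 0 | 2.8% | 2.7% | 3.0% |
| | 0.5 | 3.7% | 3.9% | 2.2% |
| | 1 | 4.2% | 4.4% | 1.8% |
| | 2 | 5.0% | 5.3% | 1.5% |

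Repeat simulations put the range for k = 0.5 to 2 at about 3.3% to 4.8% (Total) and 3.3% to 5.4% (Treated), and at 2.6% to 2.9% for Poisson counts.

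**Cause.** Poisson counts carry the same uncorrected standard error and normal quantile, yet exceed 2.5% by only 0.1 to 0.4 points. The rest of the excess grows with k while the opposite tail shrinks, which is the mark of skew. It fades slowly with n: at 5 versus 8 and k = 2, about 4.6% at n = 70, 4.1% at n = 100 and 3.6% at n = 200.

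**Superiority boundary.** At 5 versus 5 and 4 versus 4, size is 2.3% to 2.9%.

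**Correlation option.** With equal follow-up, independence and unstructured give identical results. With varying follow-up (5,000 trials; Monte Carlo SE about 0.3 points, so compare within pairs rather than reading levels), independence versus unstructured gives 4.0% versus 4.0% and 5.1% versus 5.0% (Total, k = 1 and 2), and 4.2% versus 4.2% and 5.9% versus 5.9% (Treated). The median change in the upper bound is below 0.005 bleeds/year.

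**Effect of a correction.** Mancl-DeRouen variance with t(n-1) gives about 3.2% to 3.8% at k = 1. The half-width factor with equal follow-up is t(0.975, 49)/1.96 × 50/49 = 2.010/1.96 × 1.020 = 1.046. At n = 70 it is 1.995/1.96 × 70/69 = 1.033.

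**The case against.** Several points on the other side are fair.

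- *The plan contains no wrong sentence about the interval.* Appendix 1.2 is labelled an example, SAP 6.1.1.1 says only that the interval is derived from the model, and the sandwich variance, normal quantile and independence default are software behaviour that neither document states. This stands, and the point is therefore limited to the analysis run as coded. But no other interval is specified, so the omission decides what will be run.
- *The Treated ABR figures are for that test alone.* It is reached only after steps 1 and 2 succeed. If treated bleeds go from 4 to 7 within a total of 5 to 8, with untreated bleeds unchanged, false success on both ABR tests is 2.7%, 3.5% and 4.4% for k = 0.5, 1 and 2, against 3.6%, 4.3% and 5.1% for Treated ABR alone in the same simulation. If untreated bleeds rise by 1 per year, the joint rate is 0.4% to 1.5%. It reaches the standalone value only if untreated bleeds fall, and the FVIII activity test at step 2, not counted here, can only lower it. This stands.
- *The proposed correction does not restore 0.025.* True, because it addresses the smaller cause. It still moves the size toward the stated value at little cost.
- *The margin is remote from the planned truth.* At 5 versus 2 and k = 1, the postinfusion rate variance is (2.07 + 2.07²)/1.035² = 5.9, the covariance is 0.2 × √(35.0 × 5.9) = 2.9, and SE = √((35.0 + 5.9 − 5.8)/50) = 0.84. The planned difference of −3 lies 6/0.84 = 7.2 standard errors below the margin. This stands.

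A reader might infer that the missing correlation option causes the excess, or that a noninferiority finding would be unsafe. Neither follows: the size is the same under both correlation structures, and planned power is intact.

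**Conclusion.** The stated 0.025 is not what the coded interval delivers at the noninferiority margin under the SAP's own negative binomial assumption. For k = 0.5 to 2 with 50 participants, the Total ABR size is about 1.3 to 1.9 times nominal (3.3/2.5 to 4.8/2.5), and the Treated ABR test taken alone reaches about 2.2 times (5.4/2.5). These figures rest on an assumed k, gamma frailty, a correlation of about 0.2 and a true difference of exactly 3. Near-Poisson counts would leave little to correct. Other frailty shapes of the same variance gave up to 5.6% for Total ABR, but the SAP does not assume those shapes, so they are not part of the finding.

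The matter is one of accurate error control for a result that falls near the margin. It does not threaten the noninferiority conclusion at the planned rates, and superiority is about nominal. The mismatch between Appendices 1.1 and 1.2, and the random-effect wording beside a GEE, are real but editorial.

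**What to change.** Before database lock:

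1. Name a small-sample interval for the ABR difference, for example Mancl-DeRouen variance with a t(n-1) quantile. Use it for noninferiority of Total and Treated ABR, for superiority of both, and for the reported 95% CI, so that one method serves all of them.
2. State that it reduces but does not remove the excess. Report the simulated size at the margin over a stated dispersion range (for example k = 0 to 2), and describe 0.025 as nominal for these tests.
3. Editorial: in Appendix 1.2 write `repeated subject=subjid / withinsubject=trt type=un;` to match Appendix 1.1, and delete the random-effect wording in 6.1.1.1.

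Cost: one SAP paragraph, one code line, one phrase and a small simulation. With equal follow-up the interval is about 4.6% wider at n = 50 and 3.3% wider at n = 70. Noninferiority power stays at or above 95% for k up to 7, and is at least 99.8% for Total ABR with k up to 2. Superiority becomes slightly conservative (size 1.8% to 2.4%). For k up to 2 it loses at most 2.8 points of power for Total ABR (for example 86.0% to 83.6% at k = 2) and 0.4 points for Treated ABR.
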